7.1 Primary Objective

The primary objective of this study is to evaluate the safety and tolerability of mavoglurant when used in combination with a moderate dose of alcohol in healthy social drinkers.

Specific Aim 1: To evaluate the effect of mavoglurant on blood chemistries, urine toxicology and physiological safety measures before and after alcohol administration.

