8.1 General Design Description

Double blind placebo-controlled trial of mavoglurant vs. placebo in light social drinkers (i.e., consuming 1- 6 standard alcoholic drinks per week and having engaged in at least one and no more than 12 binge drinking episodes in the past year). Participants will not meet criteria for a DSM-V Alcohol Use Disorder and must be willing to abstain from alcohol during the outpatient medication treatment phase. We propose to recruit 40 male and female social drinkers (to achieve a completer sample of 28 participants).

Subjects will sign informed consent and eligibility will be determined. Eligible subjects will participate in two alcohol administration lab sessions. They will be randomized to receive either 200 mg/day of mavoglurant or placebo for 7-10 days (14 in each study arm). During the outpatient medication administration phase, subjects will be observed daily as their medication is administered. Adverse events will be assessed. The first lab session will occur on Day 0 (prior to start of study medication) and the second lab session will occur following 7-10 days (as scheduling permits) of study medication. During each lab session, subjects will receive six successive doses of alcohol over a 90-min period designed to raise their blood alcohol levels to 80 mg/dl. Outcomes will include adverse events (during outpatient period and the lab session), safety labs (before and after drug and after alcohol), PK/PD of drug and alcohol, behavioral tests of cognition and body sway as well as self-reports of intoxication and other alcohol effects. Study staff will check in with subjects on the two days following the second lab session and an in-person follow up appointment will be scheduled 1 week after the second lab session.

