At 2pm, subjects will be given lunch and will be monitored for any remaining alcohol effects. BAC levels will be taken every 30 minutes until the level falls to less than .02 (about 4 hours). Participants will be allowed to leave when their BAC falls to below .02 or at 6pm, whichever comes first. All participants will be provided with transportation to and from lab session.

Outpatient Treatment

At the commencement of drinking session 1, participants will be sent home with the study medication for the full period. If their second lab session is not scheduled within the designated timeframe, the participant will come in for their first medication appointment and be sent home with their medication that day. They will take their medication daily (in person or on video chat – 10min) at approximately 10am. They will be observed taking the study medication, for 7-10 days (to achieve steady state levels). This will ensure compliance with medication and allow us to monitor side effects daily. The last dose of study medication will be at 8:15 on the morning of their Lab Session 2. Participants will be asked to abstain from alcohol during the outpatient medication period; our rationale for requiring this is because this is a study to examine alcohol-drug interactions and we want to study these interactions in a controlled laboratory session.

Lab Session 2

See appendix for detailed procedure sheet. Participants will arrive at the Hospital Research Unit (HRU), Church Street Research Unit (CSRU), or Masonicare at 8:15am. They will be instructed to take their last dose of study medication. We will collect BAC, urine toxicology, and provide them with breakfast. Following breakfast, they will complete study assessments/questionnaires. We will put an IV catheter in the participant's arm at 11:00am and we will draw the initial set of labs. At 12:00pm, participants will be given their first drink of 80-proof vodka with a non-carbonated mixer of their choice and will be instructed to drink it in 15 minutes. They will continue to receive successive doses of alcohol in 6 equal portions (every 15 minutes) over a 90-min period designed to raise their blood alcohol levels to 80 mg/dl. Safety labs will be drawn and blood samples will be collected at regular intervals (at baseline and every 15 minutes during the lab session and then hourly for the next 3 hours) to assess blood alcohol levels and to assess Mavoglurant levels. They will complete paper

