9.5 Planned Analyses

9.5.1 Primary Objective Analysis

Adverse events will be tabulated and rated for severity (mild, moderate, and severe) and for relation to the study intervention (unlikely, possibly, probably, and likely). Area under the curve will be measured for blood alcohol levels and compared between the two sessions (mavoglurant; baseline no-drug). Changes in serum chemistries, blood cell counts, and urinalysis will be compared before and after alcohol consumption between sessions (on drug, baseline no-drug). Quantitative outcomes will be analyzed using mixed models.

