9.5.3 Exploratory Objectives Analyses (if applicable)

Changes in subjective and cognitive motor performance measures following alcohol consumption will also be compared between sessions (on drug, baseline no-drug).

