9.5.4 Safety

Not Applicable. Evaluation of safety is already a main object for this study.

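### On its plain reading, the only laboratory comparison in Section 9.5.1 cancels a mavoglurant effect already present before the Session 2 alcohol, names no placebo comparison, and probably cannot be formed for Session 1

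*Combined protocol and SAP*

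**What the plan says.** Specific Aim 1 (Section 7.1) is "To evaluate the effect of mavoglurant on blood chemistries, urine toxicology and physiological safety measures before and after alcohol administration". Section 8.1 lists among the outcomes "safety labs (before and after drug and after alcohol".

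The planned laboratory analysis is one sentence in Section 9.5.1: "Changes in serum chemistries, blood cell counts, and urinalysis will be compared before and after alcohol consumption between sessions (on drug, baseline no-drug". The model is given only as "Quantitative outcomes will be analyzed using mixed models", with no terms or contrasts. Section 9.5.3 uses a similar construction for the exploratory measures: "Changes in subjective and cognitive motor performance measures following alcohol consumption will also be compared between sessions (on drug, baseline no-drug".

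No other section adds a laboratory comparison. Section 9.5.2 covers drug levels, Section 9.5.4 reads "Not Applicable. Evaluation of safety is already a main object for this study", Section 9.5.5 compares the arms on demographics, and Section 9.5.10 compares them on dropout.

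On timing, Section 9.3 says of the outpatient phase: "They will be observed taking the study medication, for 7-10 days (to achieve steady state levels". In Lab Session 2 the last dose is taken at 8:15, and then "We will put an IV catheter in the participant's arm at 11:00am and we will draw the initial set of labs". Alcohol starts at 12:00.

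**The concern.** By 11:00 on the day of Session 2 a participant on active drug has had 7-10 days of mavoglurant. Any effect of the drug on liver enzymes, creatinine or blood counts that develops during dosing is therefore in the pre-alcohol panel. A comparison of changes across alcohol treats that panel as its baseline, so it measures only what alcohol adds differently on drug, which is the interaction. The drug's own effect, which Aim 1 asks about before alcohol as well as after it, would have no named contrast.

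This is the only laboratory analysis planned for the primary safety objective, and the pilot is meant to supply effect sizes for later studies. A sustained laboratory shift from dosing could sit in the data while the planned comparison returned an expected value of zero.

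The comparison is also framed between sessions. A session difference mixes the drug's effect with anything else that differs between the two days. The randomised placebo arm is there to remove that, but the laboratory sentence does not mention it.

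**Working it through.** The plan states no alpha, power or effect size for this comparison (Section 9.4.1), so there is no figure to reproduce. The check has three parts.

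**1. What the contrast estimates**

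Let *d* be the drug shift present before the Session 2 alcohol and persisting after it, *a* the alcohol effect, *g* the drug-by-alcohol interaction and *s* a shift between sessions unrelated to drug. In the mavoglurant arm, relative to the Session 1 pre-alcohol value:

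- pre1 = 0; post1 = *a*
- pre2 = *d* + *s*; post2 = *d* + *s* + *a* + *g*

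The placebo arm is the same with *d* = *g* = 0.

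| Contrast | Formula | Estimates |
|---|---|---|
| 9.5.1, plain reading | (post2 − pre2) − (post1 − pre1) | *g* |
| Sessions compared before alcohol, active arm only | pre2 − pre1 | *d* + *s* |
| Same, active minus placebo | (*d* + *s*) − *s* | *d* |
| post2 − pre1, active minus placebo | (*d* + *s* + *a* + *g*) − (*s* + *a*) | *d* + *g* |
| post2 − pre2, active minus placebo | (*a* + *g*) − *a* | *g* |

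Illustrative values:

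- *d* = 10, *a* = 3, *g* = 0, *s* = 0: the 9.5.1 contrast is 3 − 3 = 0, and pre2 − pre1 is 10.
- Same with *g* = 2: the 9.5.1 contrast is 5 − 3 = 2.
- *d* = 10, *s* = 4: pre2 − pre1 in the active arm is 14. Subtracting placebo gives 14 − 4 = 10.

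Comparing the arms on the 9.5.1 contrast would not bring *d* back, since it has already cancelled within each active participant.

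**2. Which panels exist**

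- Section 6.1.1, blood volumes: a chemistry panel is 50 cc, blood alcohol samples are 5.5 cc per session, and a drug-level sample is 15 cc. Session 1: 50 + 5.5 + 15 = 70.5 cc. Session 2: 50 + 5.5 + 2 × 15 = 85.5 cc. Both match the stated volumes, so each session has room for one chemistry panel. The total, 50 + 70.5 + 85.5 + 50 + 50 = 306 ml, also matches.
- Section 11, procedure sheet: the health profile is drawn once, at 11:00, before alcohol. Later draws are for blood alcohol only.
- Sections 9.3.1 and 9.3.5: a morning-after panel is listed for Session 2 only.
- Section 9.2(h): panels on the morning after the lab sessions, in the plural. Section 9.3 also mentions safety labs loosely alongside the serial alcohol samples.

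If the volumes, schedule and procedure sheet govern, post1 is not collected and the Session 1 change cannot be calculated. The pre-alcohol panel is then the only lab-session chemistry panel paired across sessions.

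**3. Precision of the missing contrast (illustrative)**

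Section 8.1 gives 14 per arm. Assume a two-sided alpha of 0.05, a 1 between-person SD shift and session-to-session correlation *r*; the documents give none of these. The SD of pre2 − pre1 is √(2(1 − *r*)) between-person SDs. The 95% half-width for the arm difference is 2.056 × √(2/14) = 0.777 SD of the change.

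| *r* | SD of change | 95% half-width (between-person SDs) | Power for a 1 SD shift (*t* test) |
|---|---|---|---|
| 0.5 | 1.000 | 0.78 | 72% |
| 0.7 | 0.775 | 0.60 | 91% |
| 0.85 | 0.548 | 0.43 | over 99% |

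The 9.5.1 contrast would reject 5% of the time for the same shift. That is the assumed alpha and follows by construction.

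**The case against.** **The wording is loose.** The sentence can be read as comparing sessions at two time points, before alcohol and after it, which would fit Aim 1. The parallel in Section 9.5.3 favours the plain reading but does not settle it, because that sentence refers only to change following alcohol. This stands. It would be too strong to say that 9.5.1 rules out a pre-alcohol comparison. But the two readings give 0 and 10 from the same data, and neither names placebo.

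**A mixed model could supply the contrast.** It could, since the data allow it. The plan lists no terms, so nothing says that it will.

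**The cancellation is constructed.** It is exact only for a shift that alcohol leaves unchanged; any part that alcohol alters appears as interaction. The detection rates rest on assumed inputs. Both points stand.

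**A harmful rise would be noticed anyway.** A reader might infer that a drug-induced laboratory abnormality would go unseen. The documents do not support that. Section 9.2.1 allows abnormal laboratory results to be graded as adverse events, Section 9.5.1 tabulates those events, the investigator reviews them after each participant, and the DSMB reviews safety reports twice a year. None of these estimates a group difference in laboratory values, which is what Aim 1 asks for.

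**It is an exploratory pilot.** That excuses low power and argues against a single deciding contrast. It does not excuse leaving the effect named in the aim without an estimate.

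**Conclusion.** The point holds in a limited form. On its plain reading, the only planned laboratory comparison estimates the interaction and drops any drug effect that is present before the Session 2 alcohol and unchanged by it. On the looser reading it compares sessions at each time point, but still without placebo, so drug and session effects stay mixed. On the volumes, schedule and procedure sheet, the Session 1 change probably cannot be formed at all; Section 9.2(h) conflicts with them, and these places must be reconciled.

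The algebraic result needs no assumption beyond a shift that persists through alcohol. The half-widths and detection rates also need the assumed alpha, correlations and shift size, and are illustrative only. A reader might conclude that the trial cannot answer Aim 1. It can: the panels needed are scheduled under either account of the timing, and what is missing is the statement of which contrasts will be estimated.

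**What to change.** In Section 9.5.1, replace the laboratory sentence with two mavoglurant-versus-placebo contrasts from the mixed model, both measured from the Session 1 pre-alcohol panel:

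1. Session 2 pre-alcohol panel minus Session 1 pre-alcohol panel (drug without alcohol).
2. Morning-after-Session-2 panel minus Session 1 pre-alcohol panel (drug plus alcohol).

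State the model terms (arm, time point and their interaction, with repeated measures within participant). Report both contrasts with 95% confidence intervals, and name neither as deciding, since the pilot has no decision rule. Keep the Session 2 change across alcohol, compared between arms, as a supporting interaction analysis; it estimates *g* without a Session 1 post-alcohol panel.

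Reconcile Section 9.2(h) and the safety-lab wording in Section 9.3 with Sections 6.1.1, 9.3.1 and 9.3.5 and the procedure sheet on when chemistry panels are drawn.

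The cost is a few sentences and two contrast statements. No extra samples or participants are needed.

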9.5.2 Secondary Objectives Analyses

Drug plasma levels for mavoglurant will be compared before and after alcohol consumption.

9.5.3 Exploratory Objectives Analyses (if applicable)

Changes in subjective and cognitive motor performance measures following alcohol consumption will also be compared between sessions (on drug, baseline no-drug).

9.5.4 Safety

Not Applicable. Evaluation of safety is already a main object for this study.

9.5.5 Analysis of Subject Characteristics

Subject demographics will be collected and reported, noting any differences between active/placebo groups.

9.5.6 Interim Analysis (if applicable)

Not Applicable

9.5.7 Health economic evaluation

Not Applicable

9.5.8 Other

Not Applicable

9.5.9 Subsets and Covariates

Not Applicable

9.5.10 Handling of Missing Data

Mixed effects models will use all available data on individuals. Dropout rates will be compared between treatment groups and reasons for dropout will be evaluated in order to inform future studies.

10 Trial Administration

10.1 Ethical Considerations: Informed Consent/Assent and HIPAA Authorization

The study will be conducted under the ethical principles as described in 45 CFR § 46.111 and ICH GCP.

At the start of the intake session, all subjects will receive an explanation of the study including its risks, benefits, and procedures, and will be given an opportunity to withdraw from the study. Following the resolution of any questions, the subject will be asked to sign the consent form, if he/she agrees to participate. The consent form also includes language required for HIPAA Authorization.

Given that this research study is not a treatment study, there are no treatment alternatives, however subjects can decline participation.

Subjects will be paid an amount that approximates \$20/hour for study visits.

10.2 Institutional Review Board (IRB) Review

The protocol will be submitted to the IRB for review and approval. Approval of the protocol must be obtained before initiating any research activity. Any change to the protocol or study team will require an approved IRB amendment before implementation. The IRB will determine whether informed consent and HIPAA authorization are required.

The IRB will conduct continuing review at intervals appropriate to the degree of risk, but not less than once per year.

A study closure report will be submitted to the IRB after all research activities have been completed.

Other study events (e.g. data breaches, protocol deviations) will be submitted per Yale's Human Investigation Committee/Human Research Protection Program policies.

10.3 Subject Confidentiality

Subject confidentiality is held in strict trust by the research team. Subject medical record review will be limited to the just the elements needed to complete the study. Only authorized HIPAA and GCP trained study team members will have access to these records.

This study has a Certificate of Confidentiality. Subjects are informed of what this means and what it covers and its limitations in the informed consent document.

Each subject will be assigned a unique study number. A master list linking the unique study number to the human subject will be maintained in a locked drawer at our offices at [name]

Data will be stored on an encrypted password protected Yale ITS managed workstation without any HIPAA identifiers. Strict confidentiality will be maintained in all records of the study by identifying subjects by code numbers. Information that is obtained in connection with this study and that can be identified with a subject will be kept confidential (subject's charts are kept in a locked room and file cabinet. Files will be kept in locked cabinets in a security system protected office. All information obtained from subjects is referred to by code number and kept in locked confidential files (subjects' paper charts are kept in an area protected with a security system, in a locked room and file cabinet). Any published results are published as group data without the use of characteristics that would identify individual subjects. We quote information only by number in conference discussions, scientific reports or publications to maintain anonymity.

10.4 Deviations/Unanticipated Problems

If the study team becomes aware of an anticipated problem (e.g. data breach, protocol deviation), the event will be reported to the Yale HIC via IRES. If deviations occur study staff will follow Yale HIC guidelines for reporting (i.e. immediately or at annual continuing review of the protocol).

10.5 Data Collection

As required by law, all reasonable efforts will be made to protect the confidentiality of subjects' protected health information, which may be shared with others to support this research, to conduct public health reporting, and to comply with the law as required (according to a HIPAA compliant research authorization form signed by the subject). Yale Staff will collect required research data through study procedures as outlined in this protocol and record it in confidential research records and protected computer files. Each subject will have a paper "research chart" created for this information, which will be kept in a locked room and file cabinet. In all study records (except for the subject's research chart which includes the subject's name and other unique identifiers and all original records received by Yale with such identifiers), subjects will be referred to by a code number (with access to codes restricted to research staff).

Data will be stored on an encrypted password protected laptop computer without any HIPAA identifiers. Strict confidentiality will be maintained in all records of the study by identifying subjects by code numbers. Information that is obtained in connection with this study and that can be identified with a subject will be kept confidential (subject's charts are kept in a locked room and file cabinet). Files will be kept in locked cabinets in a security system protected office.

All information obtained from subjects is referred to by code number and kept in locked confidential files (subjects' paper charts are kept in an area protected with a security system, in a locked room and file cabinet). Any published results are published as group data without the use of characteristics that would identify individual subjects. We quote information only by number in conference discussions, scientific reports or publications in order to maintain anonymity.

Patient health information obtained by this study is confidential and may only be disclosed to third parties as permitted by the Compound Consent and Authorization form signed by the patient or unless permitted or required by law. Medical information may be given to a patient's personal physician or other appropriate medical personnel responsible for the patient's welfare for treatment purposes as permitted by an Authorization for Access/Release of Health Information form signed by the patient. Medical records that identify subjects and the consent form signed by subjects must be available for inspection upon request by representatives of the U.S. FDA and other regulatory agencies, national and local health authorities, the study investigators, the sponsor and the sponsor's representatives and collaborators, and the local IRB. Only research personnel will have daily access to the research records.

Although considered unlikely to be encountered, limits to confidentiality such as mandatory reporting requirements for abuse of children or the elderly will be complied with. Subjects will be notified of this mandatory reporting in the consent form.

10.6 Data Quality Assurance

All study staff will be trained to ensure accurate and consistent data collection. Data will be regularly checked by the study data manager to ensure validity and completeness. In addition, all study staff will keep up to date with all Good Clinical Practice and Human Research Protection trainings.

10.7 Study Records

Study records include IRB documents (protocol, consent forms, etc), IND documents (amendments, annual reviews, etc), a study subject binder consisting of de-identified source documents/case report forms, and a separate subject folder consisting research documents that may contain identifiable information (consent documents, subject contact information, study nurse/physician notes, etc) and is kept separately under lock and key.

10.8 Access to Source Documents

Source documents will be contained in study binders. This study will use Teleforms data entry software (using specific forms that are scannable into a database). As the binders/source documents are completed, research staff will provide the study data manager with the forms. They will then be scanned, validated uploaded into study specific databases.

